The primary endpoint is ORR measured by CT or MRI using RECIST version 1.1. Tumour response assessments are performed every 8 weeks or at the time of occurrence of first clinical signs of disease progression as determined by the investigator. **Secondary endpoints** *Phase I** Pharmacokinetics, biodistribution and dosimetry For biodistribution and dosimetry of 177 Lu-3BP-227, the secondary endpoints are: a) Maximal uptake (%); maximal concentration achieved (Cmax); time post injection to achieve maximal concentration (Tmax); area under the curve (AUC) at the target lesions, discernible organs and blood; terminal t1/2 of activity concentrations in blood. b) Highest absorbed dose, specific absorbed dose to the target lesions		expectedness and frequency of AEs.
The primary endpoint is ORR measured by CT or MRI using RECIST version 1.1. Tumour response assessments are performed every 8 weeks or at the time of occurrence of first clinical signs of disease progression as determined by the investigator. **Secondary endpoints** *Phase I** Pharmacokinetics, biodistribution and dosimetry For biodistribution and dosimetry of 177 Lu-3BP-227, the secondary endpoints are: a) Maximal uptake (%); maximal concentration achieved (Cmax); time post injection to achieve maximal concentration (Tmax); area under the curve (AUC) at the target lesions, discernible organs and blood; terminal t1/2 of activity concentrations in blood. b) Highest absorbed dose, specific absorbed dose to the target lesions		Phasa II
version 1.1. Tumour response assessments are performed every 8 weeks or at the time of occurrence of first clinical signs of disease progression as determined by the investigator. Secondary endpoints Phase I Pharmacokinetics, biodistribution and dosimetry For biodistribution and dosimetry of 177 Lu-3BP-227, the secondary endpoints are: a) Maximal uptake (%); maximal concentration achieved (C _{max}); time post injection to achieve maximal concentration (T _{max}); area under the curve (AUC) at the target lesions, discernible organs and blood; terminal t _{1/2} of activity concentrations in blood. b) Highest absorbed dose, specific absorbed dose to the target lesions		
time of occurrence of first clinical signs of disease progression as determined by the investigator. Secondary endpoints Phase I Pharmacokinetics, biodistribution and dosimetry For biodistribution and dosimetry of ¹⁷⁷ Lu-3BP-227, the secondary endpoints are: a) Maximal uptake (%); maximal concentration achieved (C _{max}); time post injection to achieve maximal concentration (T _{max}); area under the curve (AUC) at the target lesions, discernible organs and blood; terminal t _{1/2} of activity concentrations in blood. b) Highest absorbed dose, specific absorbed dose to the target lesions		
the investigator. Secondary endpoints Phase I Pharmacokinetics, biodistribution and dosimetry For biodistribution and dosimetry of ¹⁷⁷ Lu-3BP-227, the secondary endpoints are: a) Maximal uptake (%); maximal concentration achieved (C _{max}); time post injection to achieve maximal concentration (T _{max}); area under the curve (AUC) at the target lesions, discernible organs and blood; terminal t _{1/2} of activity concentrations in blood. b) Highest absorbed dose, specific absorbed dose to the target lesions		
Secondary endpoints Phase I Pharmacokinetics, biodistribution and dosimetry For biodistribution and dosimetry of ¹⁷⁷ Lu-3BP-227, the secondary endpoints are: a) Maximal uptake (%); maximal concentration achieved (C _{max}); time post injection to achieve maximal concentration (T _{max}); area under the curve (AUC) at the target lesions, discernible organs and blood; terminal t _{1/2} of activity concentrations in blood. b) Highest absorbed dose, specific absorbed dose to the target lesions		
Phase I Pharmacokinetics, biodistribution and dosimetry For biodistribution and dosimetry of ¹⁷⁷ Lu-3BP-227, the secondary endpoints are: a) Maximal uptake (%); maximal concentration achieved (C _{max}); time post injection to achieve maximal concentration (T _{max}); area under the curve (AUC) at the target lesions, discernible organs and blood; terminal t _{1/2} of activity concentrations in blood. b) Highest absorbed dose, specific absorbed dose to the target lesions		
Pharmacokinetics, biodistribution and dosimetry For biodistribution and dosimetry of ¹⁷⁷ Lu-3BP-227, the secondary endpoints are: a) Maximal uptake (%); maximal concentration achieved (C _{max}); time post injection to achieve maximal concentration (T _{max}); area under the curve (AUC) at the target lesions, discernible organs and blood; terminal t _{1/2} of activity concentrations in blood. b) Highest absorbed dose, specific absorbed dose to the target lesions		
For biodistribution and dosimetry of ¹⁷⁷ Lu-3BP-227, the secondary endpoints are: a) Maximal uptake (%); maximal concentration achieved (C _{max}); time post injection to achieve maximal concentration (T _{max}); area under the curve (AUC) at the target lesions, discernible organs and blood; terminal t _{1/2} of activity concentrations in blood. b) Highest absorbed dose, specific absorbed dose to the target lesions		
are: a) Maximal uptake (%); maximal concentration achieved (C _{max}); time post injection to achieve maximal concentration (T _{max}); area under the curve (AUC) at the target lesions, discernible organs and blood; terminal t _{1/2} of activity concentrations in blood. b) Highest absorbed dose, specific absorbed dose to the target lesions		
 a) Maximal uptake (%); maximal concentration achieved (C_{max}); time post injection to achieve maximal concentration (T_{max}); area under the curve (AUC) at the target lesions, discernible organs and blood; terminal t_{1/2} of activity concentrations in blood. b) Highest absorbed dose, specific absorbed dose to the target lesions 		
injection to achieve maximal concentration (T _{max}); area under the curve (AUC) at the target lesions, discernible organs and blood; terminal t _{1/2} of activity concentrations in blood. b) Highest absorbed dose, specific absorbed dose to the target lesions		
 (AUC) at the target lesions, discernible organs and blood; terminal t_{1/2} of activity concentrations in blood. b) Highest absorbed dose, specific absorbed dose to the target lesions 		
activity concentrations in blood. b) Highest absorbed dose, specific absorbed dose to the target lesions		
b) Highest absorbed dose, specific absorbed dose to the target lesions		
(-) 1), -r asserted asserted (5), 52-1) and camalative		
absorbed organ doses (Gy).		
For PK of 3BP-227, the secondary endpoints are:		
c) Pharmacokinetic parameters including, but not limited to, C _{max} , AUC,		
t _{1/2} , clearance (CL), volume of distribution (V _d), cumulative amount of		

unchanged drug excreted into the urine (Ae), renal clearance of the drug from plasma (CL_R), as measured in plasma and urine at defined timepoints.

Pharmacodynamic/efficacy

- a) Objective response rate and disease control rate (DCR), as determined by RECIST version 1.1 in subjects who received IMP.
- b) Progression-free survival (PFS) and overall survival (OS) rates as determined from start of study treatment until occurrence of event and/or end of observation period.
- c) Evaluation of metabolic tumour response using PERCIST (version 1.0) or practical PERCIST.
- d) Changes in serum tumour markers relevant and specific to the underlying tumour disease from Day of the first treatment administration to EOCT, which is planned 6 weeks after the second ¹⁷⁷Lu-3BP-227 dose administration.

Phase II

Efficacy

- a) Disease control rate, time to progression, time to response, duration of response as per RECIST version 1.1.
- b) Qualitative and quantitative changes in tumour-to-background uptake using PERCIST version 1.0.
- c) Progression-free survival (PFS) and OS as determined from start of study treatment until occurrence of event and/or 6 and 12 months after start of study treatment.
- d) Changes in serum tumour markers relevant and specific to the underlying tumour disease from baseline to EOCT.

Subject Reported Outcomes

a) Changes in health-related quality of life scores from baseline to EOCT measured by validated questionnaires.

Safety

a) Safety and tolerability measured by the type, severity, expectedness and frequency of AEs.

Pharmacokinetics, biodistribution and dosimetry

 For PK, biodistribution and dosimetry, the endpoints will be similar as for phase I.

Exploratory endpoints

Phase I/II

- a) Tumour uptake of ¹⁷⁷Lu-3BP-227 and the correlation with NTSR1 expression on tumour biopsies.
- b) If applicable, tumour microenvironment and other markers of interest (such as NTSR1 expression, Ki67, gene expression and DNA damage) in tumour biopsies taken at baseline, at EOCT visit or at disease progression, whichever occurs earlier.
- c) Genomic profiling in circulating cfDNA and in germline DNA.
- d) Gene mutation status in correlation with clinical outcome.
- e) Specific renal safety biomarkers specific for proximal tubulus toxicity. *Biobanking (optional):*

Serum and whole blood ribonucleic acid samples will be stored for further biomarker analysis after the end of the study. Analysis of additional biomarkers from the biobank samples will be performed outside the scope of the main study and reported separately.

Statistical methodology

Statistical methodology in phase I

Safety

Continued monitoring of DLTs and toxicities will be performed during dose escalation. At the time of the SRC, an interim analysis of the DLTs, toxicities

and selected organ absorbed doses (kidney, liver and bone marrow) will be performed to guide the dose selection during the dose escalation part.

Biodistribution, radiation dosimetry, PK of ¹⁷⁷Lu-3BP-227

Descriptive summaries of PK and biodistribution parameters will be presented for each cohort over the treatment period.

Pharmacokinetics of 3BP-227

If 3BP-227 levels are measurable in plasma and urine, PK parameters of 3BP-227 will be derived using a noncompartmental approach. An attempt to build an integrated model taking into account PK, dosimetry, antitumour and safety data will be made.

Pharmacodynamics/Efficacy Analysis

In order to perform preliminary antitumour activity, ORR and DCR will be tabulated. Tumour response will be evaluated by the site investigator. Independent review of tumour assessment may be requested at the discretion of the sponsor. In both cases, response and progression will be evaluated using the revised RECIST guideline (version 1.1). Only subjects with measurable disease at baseline, who have received at least two administrations of ¹⁷⁷Lu-3BP-227 and reached the end of Cycle 2 or EOCT visit will be considered evaluable for response.

Statistical methodology in phase II

Efficacy Analysis

For phase II cohorts, tumour response will be assessed in imaging modalities of CT or MRI scans after Cycle 2 and subsequently every 8 weeks for the first 6 months and every 12 weeks thereafter. Images will be reviewed by an independent central review core laboratory. ORR, best overall response (BOR) and other efficacy parameters will be tabulated. Objective response rate will be calculated combining the number of subjects with a BOR of confirmed complete response (CR) or partial response (PR) per RECIST version 1.1.

For the Simon Two-Stage design, the hypotheses that will be tested for each cohort are: H_0 : $ORR \le ORR_0$ versus the alternative H1: $ORR > ORR_0$ where ORR is the true objective response rate following ^{177}Lu -3BP-227 treatment that warrants further clinical development, and ORR_0 is the minimum objective response rate to be excluded from further clinical development. The thresholds for ORR and ORR_0 may be updated based on results from phase I and the evolving scientific knowledge.

Objective response rate will be analysed at the end of Stage 1 (and no later than after the 16-week visit of the last evaluable subject of the Stage 1 cohort for each PDAC and CRC cohort). If the observed number of responders is below a predefined threshold, the respective study cohort will be stopped for futility. Otherwise, additional subjects will be treated to complete the planned enrolment. At the end of Stage 2, the null hypothesis will be rejected depending on the total observed number of responders based on a predefined threshold.

At the end of phase II, descriptive summaries will be provided for all primary and secondary efficacy endpoints. For the primary endpoint, final analysis will take into account the sequential sampling procedure of the design and the underlying binomial distribution assumed by the Simon Two-Stage design.

Safety

Descriptive statistics will be calculated on the safety parameters. No formal statistical analyses of safety data are planned.

Biodistribution, radiation dosimetry, PK of ¹⁷⁷Lu-3BP-227 and 3BP-227 Analysis will be performed as for phase I.

TABLE OF CONTENTS

RAT	IONALE F	OR PROTOCOL AMENDMENT #7	. 19
LIST	r of defin	NITIONS AND ABBREVIATIONS	. 22
1		OUND INFORMATION	
1.1	Introducti	on	. 27
1.2	Name and	Description of the Investigational Medicinal Product	. 27
1.3	Nonclinica	l Data	. 27
	1.3.1	In Vitro Studies	. 27
	1.3.2	Toxicology	
	1.3.3	Pharmacokinetic Properties of Unlabelled 3BP-227	
	1.3.4	Biodistribution and Dosimetry of Radiolabelled 3BP-227	. 28
	1.3.5	Pharmacodynamic Effect In Vivo Study	. 29
1.4	Clinical Da	ata	. 29
1.5	Rationale	for the Study	. 30
1.6	Selection o	f Dosage	. 32
1.7	Population	to be Studied	. 34
1.8	Known an	d Potential Risks to Human Subjects	. 35
2	STUDY H	YPOTHESIS	. 37
2.1			
2.2			
3	STUDY O	BJECTIVES	. 38
3.1	Primary O	Objectives	. 38
	3.1.1	Phase I	
	3.1.2	Phase II	. 38
3.2	Secondary	Objectives	. 38
	3.2.1	Phase I	
	3.2.2	Phase II	. 38
3.3	Explorator	ry Objectives	. 38

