Of note, for each cohort in the dose escalation part, if a subject has clinical benefit and an acceptable tolerability profile, and if the organ dose limits are not exceeded, up to four additional cycles of ¹⁷⁷Lu-3BP-227 can be administered every 4 weeks after the end of the core trial (EOCT). The safety data evaluation will be conducted by the sponsor. The decision to administer additional cycles is based on the investigator's judgement and subject's discretion and must be discussed with and agreed upon by the sponsor.

The MTCA is defined as the maximum tolerated cumulative activity that may be administered following fractionated i.v. administrations of at least 4 weeks apart, so that:

- No more than 33% of the subjects experience a dose limiting toxicity (DLT) during Cycles 1 and/or 2 and
- The cumulative radiation in each target organ does not exceed the acceptability limits.

The DLTs are defined for any of the following IMP-related AEs according to National Cancer Institute - Common Terminology Criteria for Adverse Events (NCI-CTCAE) scale version 5.0, that occur during the defined DLT assessment period (from the first administration of ¹⁷⁷Lu-3BP-227 to EOCT/ED):

- Grade 4 neutropenia for seven or more consecutive days;
- Febrile neutropenia or neutropenic infection (defined as a documented infection with neutrophil count decreased Grade 3 or 4);
- Grade 3 or 4 thrombocytopenia (platelet count decreased) with clinically meaningful bleeding (i.e. requiring urgent hospitalisation or transfusion to manage the bleeding);
- Grade 4 thrombocytopenia for seven or more consecutive days;
- Any Grade 3 anaemia (Hb<8.0 g/dL; transfusion indicated) or Grade 4 anaemia (life-threatening consequences; urgent intervention indicated);
- Any Grade 3 or higher laboratory abnormalities in aspartate aminotransferase/alanine aminotransferase (AST/ALT) with accompanying Grade 2 or higher bilirubin (Hy's law);
- Any Grade 3 or higher renal injury/toxicity (estimated glomerular filtration rate (eGFR) <30 mL/min/1.73 m²);
- Any Grade 3 or higher GI AE, not resolved to Grade ≤2 within 48 hours despite optimal adequate medical management, with the following specifications:
 - Grade 3 nausea, vomiting (inadequate oral caloric or fluid intake; tube feeding, total parenteral nutrition or hospitalisation indicated)

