4.2 Phase I

4.2.1 Dose Escalation

Phase I will consist of a radioactivity escalation part with the objective of determining the MTCA. For phase I, subjects enrolled will have unresectable, locally advanced or metastatic tumours expressing NTSR1 originating from either the pancreas (PDAC), colon and rectum (CRC), stomach (GC), gastrointestinal stromal tumours (GIST), head and neck region (SCCHN) or bone (ES).

The study screening period includes a screening administration of ¹⁷⁷Lu-3BP-227 to assess the tumour uptake of each subject by whole body scan (planar scintigraphy, 1 or 2 timepoint(s) at the investigator's discretion) and optional single photon emission computed tomography (SPECT)/CT scans (up to 2 at the investigator's discretion). Only subjects with a tumour uptake higher than nontumoural surrounding tissue (based on investigator's decision) will be deemed eligible for treatment. The screening period will last 3 weeks but can be extended by up to 2 weeks if this is required for logistical reasons. Subjects who participated in the imaging study, Study D-FR-01087-002, with ¹¹¹In-3BP-227 (also called ¹¹¹In-IPN01087) and who have an uptake of ¹¹¹In-3BP-227 in tumour lesions that is more avid than in the nontumoural surrounding tissue based on whole body imaging (planar scintigraphy), as judged by the investigator, can also be considered for enrolment in this study, provided that they fulfil all other inclusion criteria and do not meet any of the exclusion criteria and were imaged with ¹¹¹In-3BP-227 before the first treatment administration (therapeutic dose) of ¹⁷⁷Lu-3BP-227.

During the treatment phase, it is planned that each subject will receive ¹⁷⁷Lu-3BP-227 fractionated into two i.v. administrations separated by 4 to 5 weeks (+4 weeks in case of reversible AEs) (Figure 1). The safety evaluation will be done over 4 weeks between Cycle 1 and Cycle 2 and over 6 weeks between Cycle 2 and end of core trial (EOCT). During this period, subjects will have repeated imaging for the calculation of individual dosimetry data and will be monitored for signs of toxicity.

Tumour response will be assessed on CT or MRI, as well as with ¹⁸F-FDG-PET scans at the EOCT visit, (corresponding to 6 weeks after the second administration).

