4.7.1.2 Procedures for Subject Discontinuation

For subjects who discontinue participation in the study before the planned completion of therapy, it is intended that full end of study (EOS) assessments (see Section) will be performed and the subjects will be followed-up for AEs until the event or its sequelae resolve or stabilise at a level acceptable to the investigator and the sponsor's clinical monitor or his/her designated representative (see Section 8). If a subject drops out or is discontinued from the study after IMP administration and before planned study completion (either during the Core Trial period or if the subject is receiving additional treatment cycles), an ED visit will take place within 14 days after ED. The investigator determines this timepoint taking into account the expected safety profile and the current clinical status of the subject. This visit will correspond to an EOCT visit (or EOAC visit if the subject dropout during additional cycles). Thereafter, follow-up for survival information will take place every three months. For those subjects with ED, every effort should be made to perform a safety follow-up at the latest 5 weeks after the last IMP administration.

The reason for and date of withdrawal from the study must be recorded in the electronic case report form (eCRF).

If the discontinuation is based on subject decision, every attempt will be made to determine:

- The reason for discontinuation:
- Whether the subjects also decided to withdraw consent for the sponsor to collect and use the data collected up to the discontinuation point.

Data collected prior to subject discontinuation may be kept in study records and shared with the sponsor for study analyses (see Section 13), unless a subject formally specifies their decision to withdraw consent for the use of data collected before discontinuation.

Subjects withdrawn from the study for unacceptable AE(s) will be followed until resolution or stabilisation of the AEs.

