4.7.1.3 Replacement Rules

In phase I, a cohort will be considered as completed once three subjects of the cohort complete Cycle 2 or discontinue early during Cycle 2 (except for Cohort 1). Except for Cohort 1, if subjects discontinue for any reason other than a DLT (e.g. disease progression) before end of Cycle 2, they may be replaced.

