8.1.1 Definition of an Adverse Event

An AE is the development of an undesirable medical condition or the deterioration of a pre-existing medical condition, whether or not considered causally related to the product. An undesirable medical condition can be symptoms (e.g. nausea, chest pain), signs (e.g. tachycardia, enlarged liver) or the abnormal results of an investigation (e.g. laboratory findings, ECG).

An AE can include an undesirable medical condition occurring at any time, even if no IMP has been administered. All AEs, irrespective of causality, are to be reported to the sponsor up to 6 months after the EOCT, ED or EOAC visit or until new antitumour treatment starts, whichever comes first. After this timepoint, up to the end of the 5-year follow-up period, AEs should only be reported if the event is evaluated as related to the IMP or study procedure by the investigator.

This definition includes events occurring from the time of the subject giving informed consent until the EOS (last visit in the long term follow-up period)/ED.

Natural disease progression or deterioration of the malignancy treated in the study will be recorded as part of the efficacy evaluation. The signs and symptoms of disease progression will be documented as part of the radiological or clinical progression. Events that cannot be differentiated from progressive disease (PD) should be captured as AE/SAEs. Death due to disease progression should be reported as an SAE irrespective of causality if reported during the study period and up to 6 months after the end of the cycle of the last dose of study drug. Serious adverse events including death/fatal outcome will be reported to sponsor if evaluated as related to study treatment or procedure up to the protocol defined follow-up period and EOS.

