12.1 Analysis Sets

For dose escalation only, all subjects who complete Cycle 2 or discontinue during Cycle 1 or Cycle 2 due to a DLT will be included in the MTCA and MTSA evaluations.

For the overall study, all subjects who received at least one dose of the IMP will be included in the safety evaluation. All subjects who receive at least one dose of IMP and who have postbaseline efficacy data will be included in the efficacy evaluations. All subjects with evaluable 3BP-227 PK data and no major protocol deviation with an impact on PK analysis will be included in the evaluation of 3BP-227 PK. All subjects with evaluable dosimetry images and no major protocol deviation with an impact on dosimetry analysis will be included in the evaluation of dosimetry. All subjects with evaluable blood or urine dosimetry data and no major protocol deviation with an impact on ¹⁷⁷Lu-3BP-227 PK analysis will be included in the evaluation of ¹⁷⁷Lu-3BP-227 PK. Major deviations will be described in a specific document.

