- a the ED visit will take place within 14 days after ED from the study and at the latest 5 weeks after the last IMP administration, the visit will correspond to an EOCT visit. For subjects who received the screening IMP administration and found ineligible to participate to the study, an ED visit will be performed within 5 weeks (+ 2 weeks) after the IMP screening administration to assess the safety. At least, clinical laboratory tests (e.g. haematology and biochemistry), AEs and concomitant medication/therapy will be collected. If the subject is not able to come for an on-site visit, the visit may be performed by phone call. The clinical laboratory tests may be done locally.
- b follow-up visits will take place every 3 months (±2 weeks) and will start after the EOCT, ED or EOAC visit. Efficacy will be assessed until disease progression, administration of any other chemotherapy or radiotherapy, lost to follow-up, withdrawal of consent, death or a maximum of 2 years, whichever occurs first (see Section 6.2.3). After disease progression is confirmed, no further CT/MRI scans will be required for tumour/disease assessment. The survival status and safety of the subjects will continue to be monitored as indicated in Section 8.1.2.3 until lost to follow-up, withdrawal of consent, death or a maximum of 5 years, whichever occurs first.
- c the screening period can be extended by two weeks if this is required for logistical reasons.
- d Day 1 of Cycle 1 is the day of the first treatment administration. Day 1 of Cycle 2 and each potential subsequent cycle may coincide with Day 29 of the previous cycle if all safety assessments are performed and allow for the next administration.
- e in case of toxicity requiring a delay, the next treatment administration will be delayed by up to 4 weeks.
- f whole body ceCT or ceMRI including brain unless a similar exam has already been performed within 1 month prior to Day -21.
- g Cycle 1 Day 1 ¹⁸FDG-PET between Day -21 and Day 1.
- h screening administration will be done after confirmation of eligibility (i.e. after all other screening assessments have been performed), minimum 1 week before the first treatment administration.

Procedures and			CORE TRIAL [v]										EOCT	Long-term							
assessments	Screening		Treatment Period								or	Follow-up									
	Screening				Cycle 1					Cycle 2									ED [a]	[b]	
	D-21 to D-1	D1 [d]	D2	D3	D4	D5	D7	D 15	D 22	D29	D1 [d]	D2	D3	D4	D5	D7	D15	D22	D29	D43	

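### Protocol 12.1 builds the MTCA/MTSA set on the recorded reason for stopping, so a qualifying DLT in a subject who left for another reason is excluded; the DLT window also varies, and the bias can go either way

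*Protocol*

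**What the plan says.** **DLT period.** The synopsis and protocol 4.7.1.1 count listed IMP-related events "that occur during the defined DLT assessment period (from the first administration of ¹⁷⁷Lu-3BP-227 to EOCT/ED"). SAP 1.2 and 3.2.1.1 use the same limits.

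**When it closes.** EOCT is described in 4.2.1 as "corresponding to 6 weeks after the second administration". For a subject who leaves early, 4.7.1.2 says "an ED visit will take place within 14 days after ED", and footnote a to Table 8 (Attachment 1) adds a cap: "the ED visit will take place within 14 days after ED from the study and at the latest 5 weeks after the last IMP administration". By contrast, the model in Attachment 5 (19.5.1) describes DLTs up to 4 weeks after the two cycles.

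**Who is analysed.** For the MTCA and MTSA evaluations, 12.1 states that "all subjects who complete Cycle 2 or discontinue during Cycle 1 or Cycle 2 due to a DLT will be included". Attachment 5 (19.5.2) fits the model to whatever Cycle 1 and Cycle 2 data are available. The SAP defines no MTCA set. Its DLT table (3.2.1.1) falls under the safety population (2.3 and 3.2.1), which takes in anyone given a dose, including the screening dose. SAP Section 5 declares no changes from protocol.

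**Replacement and cohort completion.** Under 4.7.1.3, except in Cohort 1, "if subjects discontinue for any reason other than a DLT" before the end of Cycle 2 they may be replaced. Attachment 5 replaces subjects who do have a Cycle 1 DLT, up to two. Section 4.2.1.2 lets a Cycle 2 discontinuation for any reason count towards completing the cohort.

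**Data after ED.** AEs "are to be reported to the sponsor up to 6 months after the EOCT, ED or EOAC visit", or until new antitumour treatment if earlier; related events continue to be reported after that (8.1.1, 8.1.2.3).

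**The concern.** DLT incidence is a primary variable for the MTCA, so the plan needs one answer to two questions: who is in the denominator, and for how long was each subject at risk? Here the answer depends on a field in the case report form. Two subjects with the same DLT on the same day, both inside the DLT period, are treated differently if one is recorded as leaving for the DLT and the other for progression. Leaving for progression is foreseen: 4.7.1.3 gives it as an example.

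Cohorts are small, so one subject matters. A first DLT reduces the escalation increment and brings in the model (4.2.1.3), and a DLT after the first administration delays the next cohort (4.2.1.4).

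**Working it through.** I read ED as the ED visit, since it is paired with EOCT. If it meant the day of stopping, the window would be shorter still.

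**1. Window lengths, minimum schedule.**
- Completer: 28 + 42 = 70 days from first dose.
- Stops in Cycle 1: at most 35 days from first dose.
- Stops after dose 2: at most 28 + 35 = 63 days, so at least 7 days fewer than a completer.
- Completes Cycle 2 (28 days after dose 2) but leaves before EOCT: in the 12.1 set as DLT-free with 42 − 35 = 7 to 42 − 28 = 14 days unobserved.

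**2. One subject in a cohort of three.** Adding back one stopper with an uncounted DLT moves 0/3 to 1/4 (25%), or 1/3 (33%) to 2/4 (50%). Adding back a DLT-free stopper moves 1/3 to 1/4. The two corrections go in opposite directions.

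**3. Direction in general.** Suppose a fraction d of subjects is excluded. Let q1 be the DLT risk in those retained and q2 the risk in those excluded. The 12.1 rate is q1, the all-subject rate is (1 − d)q1 + d·q2, and the bias is d(q1 − q2). With d = 0.2 and q1 = 0.33, q2 = 0.5 gives −3.4 points and q2 = 0.2 gives +2.6 points. The sign depends on whether excluded subjects are at higher or lower risk.

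**4. Closed form, stopping unrelated to DLT risk.** Assume constant hazards, a true full-window DLT rate of 33% and a non-DLT stopping probability d. The hazards are λD = −ln(0.67) = 0.400 and λS = −ln(1 − d).

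P(DLT before stop) = λD/(λD + λS) × [1 − 0.67(1 − d)]; P(complete, DLT-free) = 0.67(1 − d).

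- d = 0.10: 0.400/0.506 × 0.397 = 0.314, and 0.603. 12.1 rate = 0.314/0.917 = 34.3%.
- d = 0.40: 0.400/0.911 × 0.598 = 0.263, and 0.402. 12.1 rate = 0.263/0.665 = 39.5%.

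This is above 33% because DLT stoppers stay in while DLT-free stoppers drop out. With every treated subject in the denominator, as in the SAP table, the same inputs give 31.4% and 26.3%.

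**5. Simulation.** 1,000,000 subjects per setting; doses on days 0 and 28; ED visit 0 to 14 days after stopping, capped at 35 days after the last dose; true rate 33%; DLT onset at 1–42 or 21–42 days; a shared latent factor links DLT and non-DLT stopping. Rates in the 12.1 set:

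| Link between stopping and DLT risk | 10% stop | 25% stop | 40% stop |
|---|---|---|---|
| None, onset 1–42 | 34.0% | 35.9% | 38.5% |
| None, onset 21–42 | 33.6% | 34.7% | 36.6% |
| Moderate (0.5), onset 1–42 | 32.7% | 33.4% | 34.9% |
| Moderate (0.5), onset 21–42 | 32.1% | 31.8% | 32.1% |
| Strong (0.8), onset 1–42 | 30.8% | 29.1% | 28.6% |
| Strong (0.8), onset 21–42 | 29.9% | 26.6% | 24.5% |

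DLTs between stopping and the ED visit, which 12.1 as written drops, were 0.3% to 2.3% of treated subjects. DLTs after the ED visit were 0.9% to 10.0%. The percentage with all treated subjects as denominator was 18.7% to 31.4%, below 33% in every setting.

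**The case against.** **The exclusion is narrow.** Under 4.7.1 a DLT itself ends treatment, so a DLT in a subject still on treatment will normally be recorded as the reason and enter the set. That stands. What remains is mainly a DLT between stopping for another reason and the ED visit, 0.3% to 2.3% of treated subjects in the simulation, which is under one of 30.

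**Other parts of the plan see these events.** The SRC reviews everything accrued and takes the escalation decision (12.2.8), Attachment 5 uses all available data, and the SAP table has no filter on reason for stopping. This helps during escalation. It does not settle the MTCA evaluation: 12.1 is the only stated set for it, and the other passages contradict that set. The trial simulations describe no non-DLT dropout, so Table 13 does not cover the question.

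**A stronger reading.** A reader might infer that the DLT rate behind the MTCA is biased down and the MTCA therefore too high. The documents do not support that. Excluded stoppers leave the denominator as well as the numerator, and the sign then depends on how stopping relates to DLT risk. A consistently downward result appears for the SAP percentages, but that table is not the MTCA estimate.

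A reader might also convert the shorter window into a number of lost DLTs. That would need a phase I stopping rate, which is not given (the 20% in 12.3.1 is phase II non-evaluability), and most such subjects lie outside the 12.1 denominator.

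**Conclusion.** The point holds as a defect of definition. Section 12.1 selects on the recorded reason for stopping and can exclude an event that meets the protocol's own DLT definition. It conflicts with Attachment 5 and the SAP on who is counted, and the DLT window differs between early leavers, completers and the model.

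The size is not known. With a true rate of 33% and 10% to 40% non-DLT stopping, both assumed, the 12.1 rate runs from 24.5% to 39.5% according to how stopping relates to DLT risk and when DLTs arise. The plan gives no discontinuation rate or onset distribution, and provides no sensitivity analysis. The defect should be corrected, but it does not show that the MTCA will be set too high.

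**What to change.** 1. In protocol 12.1, and as a new set in SAP Section 2, define the DLT-evaluable set by observed status: every subject with a qualifying DLT in the DLT period whatever reason for stopping is recorded, plus every subject observed DLT-free for the whole stated window.
2. Make 4.7.1.3, the replacement rule in Attachment 5 and the cohort-completion wording in 4.2.1.2 consistent with that set, and state which data the model uses.
3. Reconcile the window passages: the synopsis and 4.7.1.1, 4.2.1, footnote a to Table 8, and 19.5.1. This review does not propose which length applies.
4. Add a sensitivity analysis that includes partly observed early leavers, for example bounding them as all DLT-free and all DLT, or weighting each by the fraction of the window observed. Use the related AEs already collected after ED. It is needed even after step 1, because that set still takes DLTs whenever they are seen but DLT-free subjects only if fully observed.

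The cost is wording in both documents and one extra analysis. Its limit should be stated: after ED the next scheduled blood tests are in three-monthly follow-up (6.2.3), and all-cause AE reporting stops at new antitumour treatment. Laboratory DLTs, such as Grade 4 cytopenias lasting seven or more days, are therefore only partly ascertained after ED, and that interval should not be treated as fully observed.
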